## **16.2.2Egg reduction**

#### Analysis set(s):

• Primary analyses will be based on the mITT and PP analysis sets.

The group/collective egg reduction rate will be determined as follows:

- ERRA (%) = relative difference expressed in percent between the post-treatment mean egg count and the pre-treatment mean egg count ((pre-treatment egg count - post-treatment egg count) / pre-treatment egg count) including all patients.
- $ERR_G$  (%) = relative difference expressed in percent between the log-transformed posttreatment mean egg count and the log-transformed pre-treatment mean egg count ((logtransformed pre-treatment egg count - log-transformed post-treatment egg count) / logtransformed pre-treatment egg count) including all patients.
  - The following log transformation will be used to calculate the geometric mean: log(x + 1)

This log transformation is required, otherwise the ERRG result would only be calculated on uncured patients only, which would introduce a bias and an important underestimation of the true ERRG.

All raw egg counts will be multiplied by four prior to use in any derivation. Missing egg counts will be imputed using the LOCF approach.

To prepare the original data for bootstrapping, missing data will be imputed, followed by random sampling of pairs (2-tuples) of baseline and end-of-study egg counts, i.e. {Kato-KatzBaseline; Kato-KatzEnd-of-Study}, using PROC SURVEYSELECT, with unrestricted random sampling, at a sampling rate of 1 and 10 000 replicates. ERRA and ERRG will be computed by *replicate*, to establish the bootstrap sample.

The arithmetic mean of the bootstrap sample will constitute the point estimate. Corresponding 95% CIs will be determined using the percentile method, based on the bootstrap sample. Point and interval estimates of  $ERR_A$  and  $ERR_G$  will be presented by cohort. Mean Kato-Katz egg counts will be listed by cohort and subject and time point. Estimates of  $ERR_A$  and  $ERR_G$  will be presented graphically in the form of boxplots, by cohort.

The  $ERR_A$  or  $ERR_G$  slopes by treatment group will be compared to determine which treatment has the fastest egg clearance rate.

Results will be presented for each analysis set.

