3.4.2 Clinical data in children

3.4.2.1 Efficacy data

A meta-analysis in children combining data from thirty-five studies identified through a systematic literature search was recently conducted [11]. In total 12,562 preschool and schoolaged children and adolescents were enrolled, of whom 91% were assessed within 8 weeks of treatment with PZQ at 40 mg/kg dose (54%) or comparators (46%). The meta-analysis showed that the overall cure rate (CR) with PZQ at 40 mg/kg dose was 75.0% (95% CI, 70.2% - 79.6%) and 76.6% (95% CI, 67.4% - 84.7%) for children infected with *S. mansoni* and *S. haematobium*, respectively (Table 1). The mean egg reduction rate (ERR) was 95% for children infected with *S. japonicum*, 94.1% for *S. haematobium* and 86.3% for *S. mansoni*. No significant relationship between dose and ERR was detected. However, the number of pre-school aged children infected with *S. mansoni* in this analysis was limited (n = 988) and this age group received only PZQ doses of 40 mg/kg.

Children age group	Species	Efficacy Number of		Number of	Mean	Bootstrap 95%Cl	
		indicator	groups	children		Lower	Upper
_	S. Mansoni	CR	12	988	79.4%	71.7%	87.1%
		ERR	9	988	76.1%	59.1%	89.4%
	S. Haematobium	CR	5	179	87.0%	81.9%	93.2%
		ERR	5	179	63.9%	35.3%	89.7%
	S. Mansoni	CR	25	3169	74.4%	68.4%	80.0%
		ERR	18	2245	85.5%	79.2%	90.9%
	S. Haematobium	CR	22	2876	73.3%	64.3%	81.3%
		ERR	19	2168	91.6%	86.3%	96.0%
	S. Mansoni	CR	37	4157	76.0%	71.4%	80.2%
		ERR	27	3233	82.4%	75.2%	88.5%
	S. Haematobium	CR	27	3055	75.9%	67.9%	82.7%
		ERR	24	2347	85.9%	77.7%	92.9%

Legend: CI, confidence interval; CR, cure rate; ERR, egg reduction rate

Table 1. Meta analysis results of cure rates and egg reduction rates after administration of single dose of 40 mg/kg rac-PZQ by age group (courtesy of [name] - personal communication).

PZQ at a single dose of 60 mg/kg was safely administered in a study recently performed in Brazil, including only few pre-school aged children. The results showed that there was no evidence of difference in effectiveness between the different age groups (Table 2).

Age (years)	N	Cure rate	95% CI
4-6	24	91.7%	67.6% - 99.1%
7-8	97	89.7%	80.1% - 95.3%
9-10	119	89.1%	80.5% - 94.4%
11-15	299	91.6%	87.2% - 94.8%

Table 2. Cure rates after administration of rac-PZQ 60 mg/kg single dose, observed in Brazilian children of different age groups infected with *S. mansoni* (courtesy of [name], Fiocruz Brazil - personal communication)

CCI

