8.2 Randomization

Part 1: Treatment allocation will be random and balanced at a ratio of 1:1:1:1:1.1. Randomization will be stratified by the infection severity (40% moderate/heavy and 60% light infections). After 20 subjects/arm are randomized, the SMC will decide on the inclusion of the 7^{th} arm.

Randomization will continue for arms C1-C6 at a ratio of 1:1:1:1:1:1 until a total of 40 subjects/arm are randomized.

If the C7 arm is included, randomization will continue with an allocation ratio of 1:1:1:1:1:3. If C7 arm is not included, the allocation ratio will remain the same (1:1:1:1:1).

Randomisation lists indicating a randomisation number and which treatment is to be given, will be produced prior to the start of the trial by the statistician at the PPD. Based on the randomisation lists sequentially numbered sealed envelopes which contain a randomisation number and the treatment allocation will be prepared. The sealed randomization envelopes will look identical and will be kept in a locked cupboard to which only the study pharmacist will have access.

Part 2: There is no randomization in this part.

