## List of Abbreviations and Definition of Terms

AE	Adverse Event
AIDS	Acquired Immunodeficiency Syndrome
ALT	Alanine Aminotransferase
ANOVA	Analysis of Variance
AST	Aspartate Aminotransferase
ATC	Anatomical Therapeutic Chemical
$AUC_{0-\infty}$	Area under the concentration-time curve (AUC) from time zero to infinity
AUC 0-t	Area under the concentration-time curve (AUC) from time zero to the last sampling time at which the concentration is at or above the lower limit of quantification
AUC extra	Extrapolated AUC from time $t_{\text{last}}$ to infinity given as percentage from $AUC_{0\text{-}\infty}$
CL/f	Apparent total body clearance of drug
Cmax	Maximum observed concentration
CNER	Comité National d'Ethique et de la Recherche
CRF	Case Report Form
CRP	C-reactive Protein
CSR	Clinical Study Report
ERR	Individual Egg Reduction Rates
ERRA	Group/Collective Egg Reduction Rate (based on arithmetic mean)
ERR G	Group/Collective Egg Reduction Rate (based on geometric mean)
ICH	International Conference on Harmonisation
IMP	Investigational Medicinal Product
PPD	PPD
LLN	Lower Limit of Normal
LOCF	Last Observation Carried Forward
LSLV	Last subject, last visit
MedDRA	Medical Dictionary for Regulatory Activities
mITT	Modified Intention-to-Treat
NCA	Non-compartmental Analysis

NCI-CTCAE	National Cancer Institute – Common Terminology Criteria for Adverse
	Events
ODT	Oral dispersible tablets
PD	Pharmacodynamic(s)
РК	Pharmacokinetic(s)
РР	Per Protocol
РТ	Preferred term
PZQ	Praziquantel
Q1	First quartile
Q3	Third quartile
SAE	Serious Adverse Event
SAF	Safety Analysis Set
SAP	Statistical Analysis Plan
SCI	Schistosomiasis Control Initiative
SD	Standard deviation
SERU	Scientific and Ethics Review Unit
SDTM	Standard Data Tabulation Model
SMC	Safety Monitoring Committee
SOC	System Organ Class
t½	Apparent terminal half-life
TEAE	Treatment Emergent Adverse Event
t.i.d.	Three times a day
tlag	Time prior to the first measurable (non-zero) concentration
TLF	Tables, Listings, and Figures
ULN	Upper Limit of Normal
tmax	Time to reach the maximum concentration
Vz/f	Apparent volume of distribution during the terminal phase
λz	Apparent terminal elimination rate constant

4 Modification History			
Unique Identifier for SAP Version	Date of SAP Version	Author	Changes from the Previous Version
1.0	01 Aug 2016	PPD	N/A

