	• Egg Reduction Rate (ERR, %) calculated based on the arithmetic (and geometric) mean egg count per gram of stool (epg) before and 14-21 days after treatment (as determined by Kato-Katz method).
	• Cure defined as absence of parasite antigens in the urine as assessed by the commercially available POC-CCA test for S. mansoni
	Safety and tolerability endpoints
	• Changes in laboratory safety parameters and vital signs (body temperature, blood pressure and pulse rate)
	• Occurrence, nature, severity and outcome of adverse events
	Occurrence of Adverse Drug Reactions per treatment group
Pharmacokinetics	Originally, a PK profile of L-PZQ, D-PZQ and rac-PZQ (AUC 0-t , $C_{max}$ , $t_{max}$ , $t_{lag}$ , AUC 0-<math>\infty</math> , AUC extra , $t_{\frac{1}{2}}$ , $\lambda_z$ , CL/f and $V_z/F$ ) was to be produced, followed by assessment in 25% of the subjects of cohorts C1-C7 with a rich sampling scheme and in 75% of the subjects with a sparse sampling scheme.
	Further, PK would have been assessed in all subjects of Part 2 (cohorts C8 and C9) with a rich sampling scheme. Due to technical challenges in the preparation of the PK samples, it was decided by the Sponsor that no PK variable calculations will be done. The data will only be listed, and not analysed.
	The planned PK analysis is pending resolution of technical problems with previously validated DBS bioanalytical assay. Depending on the outcome, the PK data may potentially just be listed and not analysed.
Diagnosis	Screening diagnosis of S. mansoni infection will be done using a single POC-CCA urine cassette test. Briefly, one urine sample will be collected from each subject and evaluated with a commercially available POC-CCA cassette test.
	Subjects who are positive for POC-CCA test will provide stool samples to assess infection intensity using the Kato-Katz method.

Subjects will be tested for S. haematobium in order to exclude S. mansoni/S. haematobium co-infections.

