## 7 Sample Size/Randomisation

## 7.1 Sample Size

Part 1: this study is exploratory. There is no hypothesis testing.

The sample size is based on the minimum number of subjects to reach a meaningful precision of the primary efficacy endpoint estimate (cure rate) in each arm, considering the stratification factor.

There are limited historical data on the impact of the severity of infection on the observed cure rate. In the recent study by Keiser et al. (unpublished data), the observed cure rate in *S. mansoni* infected children varied between 55% and 60% in moderately infected children and 70% and 85% in light infected children depending on the dose. The table below presents the overall cure rate projections according to different assumptions of true cure rate in mild (low) and moderately infected children.

Overall cure rate (95%CI),	Assump	tions of Cure F	Rate in Light In	fections
(N=50)	70%	75%	80%	85%

	50%	62% (48%, 74%)	65% (52%, 78%)	68% (56%, 80%)	71% (60%, 82%)
Assumptions of	55%	64%	67%	70%	73%
Cure Rate in		(50%, 76%)	(54%, 80%)	(58%, 82%)	(62%, 84%)
Moderate/Heavy	60%	66%	69%	72%	75%
Infections		(52%, 78%)	(56%, 80%)	(60%, 84%)	(64%, 86%)
	65%	68% (54%, 80%)	71% (58%, 82%)	74% (62%, 86%)	77% (66%, 88%)

A minimum-clinical meaningful cure rate is considered as equal to 70%. With 50 evaluable patients enrolled, stratified as 40% moderate/heavy and 60% light, the corresponding 95% CI lower bound of an observed cure rate of 70% would be above ~58%, depending on potential difference between the strata. This sample size would also provide the minimum number of subjects to estimate the cure rate within strata.

Considering the efficacy criteria for the selection of the dose (observed cure rate >70%), through simulations, the table below presents the probability of observing an overall cure rate >= 70% based on different scenarios of true cure rates based on different strata, assuming a stratification of 40% moderate/heavy infections and 60% light infections.

Probability of observ	ring a	Assumptio	ns of Cure I	Rate in Ligh	t Infections
cure rate $\geq 70\%$ , N	=50,	70%	75%	80%	85%
	50%	15%	27%	45%	64%
Assumptions of Cure Rate in	55%	23%	38%	57%	76%
Moderate/Heavy Infections	60%	33%	51%	70%	85%
intections	65%	45%	63%	80%	92%

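### SAP 16.2.2 computes the geometric-mean egg reduction rate on the log scale without back-transforming, so as written it gives a different and lower figure

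*SAP*

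**What the plan says.** SAP 16.2.2 gives ERR_G as the "relative difference expressed in percent between the log-transformed posttreatment mean egg count and the log-transformed pre-treatment mean egg count". The bracketed formula that follows takes the log pre-treatment count minus the log post-treatment count and divides by the log pre-treatment count. Beneath it the SAP adds: "The following log transformation will be used to calculate the geometric mean", namely log(x + 1), and explains that without this step only uncured children would count and ERR_G would be understated.

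The intended quantity is named elsewhere. The SAP abbreviation list has "Group/Collective Egg Reduction Rate (based on geometric mean"). The endpoint table in SAP 6.2, like Protocol 8.3.2, has the egg reduction rate "calculated based on the arithmetic (and geometric) mean egg count per gram of stool (epg) before and 14-21 days after treatment". Protocol 8.5.3 writes out a formula for the arithmetic version only. SAP section 9 says that the protocol's statistical methods were adopted, so no change of endpoint is declared.

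The same SAP section computes ERR_G in each of 10,000 bootstrap replicates and then states: "The arithmetic mean of the bootstrap sample will constitute the point estimate". It also plans to compare egg reduction slopes between treatments to see which clears eggs fastest.

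**The concern.** The mean of log(x + 1) is an intermediate step towards a geometric mean. To reach the geometric mean it must be exponentiated and 1 subtracted. The SAP forms the percentage reduction before doing that, so the stated rule and the named endpoint are different quantities.

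A programmer who follows the formula reports a secondary efficacy endpoint on the wrong scale. Because it is applied replicate by replicate, the confidence interval surrounds the wrong quantity too. The figure cannot be compared with other egg reduction rates based on geometric means. It can also fall below the arithmetic rate reported beside it when the true geometric rate lies above, and a reader comparing the two would be misled.

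**Working it through.** The documents state no numerical ERR_G, so there is no planned figure to reproduce.

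**Formulas.** Let L0 and L1 be the arm means of ln(x + 1) before and after treatment.

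- As written: 100 × (1 − L1/L0). The log base cancels.
- Reduction in geometric mean: 100 × (1 − [exp(L1) − 1]/[exp(L0) − 1]).

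**Direction, with no assumed data.** The function exp(L) − 1 is convex and equals zero at L = 0. For 0 < L1 < L0 it follows that [exp(L1) − 1]/[exp(L0) − 1] < L1/L0, so the written formula is always the lower of the two. They agree only when nothing changes or when every egg is cleared. A check of 200,000 random pairs found no exception.

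**Hand examples (assumed geometric means)**

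| Geometric mean, epg | As written | Back-transformed |
|---|---|---|
| 100 to 1 | 1 − ln 2/ln 101 = 1 − 0.693/4.615 = 85.0% | 99.0% |
| 100 to 10 | 1 − ln 11/ln 101 = 1 − 2.398/4.615 = 48.0% | 90.0% |
| 24 to 2.4 | 1 − ln 3.4/ln 25 = 1 − 1.224/3.219 = 62.0% | 90.0% |
| 400 to 40 | 1 − ln 41/ln 401 = 1 − 3.714/5.994 = 38.0% | 90.0% |

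The last three rows share a true 90% reduction, yet the written formula falls from 62.0% to 38.0% as the baseline rises.

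**Likely size in this trial**

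- From the documents: a 60/40 mix of light and moderate/heavy infection (Protocol 8.2); stratum cure rates from the table in SAP 7.1; the 91.7% cure rate at ages 4–6 in Protocol Table 2; and counts in steps of 4 epg (six smears × 41.7 mg = 250.2 mg, and 1000/250 = 4).
- Assumed: baseline geometric means of 30 epg (light) and 250 epg (moderate/heavy), SD 0.7 on the natural-log scale, and uncured children keeping 10–50% of their baseline count.

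| Cure, light / moderate-heavy | Overall cure | Shortfall of written formula, points |
|---|---|---|
| 70% / 50% | 0.6×70 + 0.4×50 = 62% | 20.1–29.7 |
| 80% / 60% | 72% | 15.6–23.1 |
| 85% / 60% | 75% | 14.5–21.5 |
| 85% / 65% | 77% | 13.1–19.6 |
| 91.7% in both | 91.7% | 4.2–6.5 |

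Repeat runs agree within 0.2 points. In the 75% row with 25% residual, L0 = 4.275 and L1 = 0.863. The written formula gives 1 − 0.863/4.275 = 79.8%. The geometric mean falls from 70.9 to 1.37 epg, which is 98.1%. The arithmetic rate in that scenario is 90.9%, so the written ERR_G lies below it and the true one above.

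**Sensitivity to the assumptions.** A wider grid (baseline geometric mean 30–400 epg, log SD 0.8–1.6, residual 5–50%) gives gaps of 9–32 points at 62–77% cure and 3.4–7.2 at 91.7%. A second model, with log-uniform baselines of 4–99 and 100–1000 epg, 85%/60% cure and residuals of 10–50%, gives 82.7–75.2% as written against 98.3–97.1%. Other literal readings of the wording are also low in that model: the log of the arithmetic mean gives 60.4–32.2%, and the mean of individual log ratios gives 84.8–78.7%.

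**Two minor points in the same section**

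- Bootstrap mean as point estimate: in 400 simulated arms of 60 it differed from the observed value by 0.12 points on average for the arithmetic rate and 0.06 for ERR_G.
- Slopes: Protocol 7.3.1 and Appendix II place Kato-Katz at baseline and days 14–21 only. Two time points cannot show speed of clearance. The inclusion criteria mention stool at 24 hours and day 8, but no Kato-Katz reading is scheduled then.

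**The case against.** The best defence is that this is loose drafting with visible intent. The line under the formula names the geometric mean, the abbreviation list and endpoint table do the same, and a geometric mean is back-transformed by definition. The neighbouring arithmetic formula is also shorthand: its bracket drops the word mean, and nobody would compute it child by child. A good programmer might therefore do the right thing. That is a fair reading of intent, but the bracketed formula is explicit, nothing elsewhere corrects it, and it is what would be coded.

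Other limits stand:

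- The trial is exploratory, ERR_G is a descriptive secondary endpoint, and the error could be repaired later from the raw counts.
- The written formula is not too low in an arm that is fully cleared, which is possible in a cohort as small as C9 (10 infants).
- The sizes above rest on egg counts that the documents do not supply; only the direction is free of assumptions.
- Distortion from baseline intensity varies. With 75% cure and 25% residual in both strata, the written value moves only from 83.9% (all light) to 81.1% (all moderate/heavy), and the back-transformed value also drifts, from 97.5% to 99.3%, because of the +1. That mildness depends on equal cure in both strata and on cure dominating. Stratified randomisation limits the effect between Part 1 arms; Part 2 is not randomised.
- The bootstrap-mean point is negligible in size.

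**Conclusion.** The concern holds. Followed literally, SAP 16.2.2 does not compute the reduction in geometric mean egg count, and it understates that reduction in any arm where the geometric mean falls but not to zero. With the assumed egg counts the shortfall is roughly 13 to 30 points at overall cure rates of 62–77% and 4 to 6.5 points at 91.7%. The conclusion is conditional on the formula being programmed as written. It should be fixed before analysis, but it does not threaten the trial's main conclusions: the primary cure rate, the arithmetic egg reduction rate, the sample size and the cure-rate criterion for dose selection do not depend on it.

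**What to change.** Replace the ERR_G definition in SAP 16.2.2 with:

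ERR_G = 100 × (1 − [exp(mean ln(post + 1)) − 1] / [exp(mean ln(pre + 1)) − 1])

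State that logs are taken per subject and then averaged within the arm, and that the whole expression is evaluated in each bootstrap replicate.

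Two small companion edits belong with it:

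- Report the observed arithmetic and geometric rates as point estimates and keep the bootstrap for the percentile interval, in line with Protocol 8.5.3.
- Delete the sentence on slopes and speed of clearance.

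The cost is a few SAP sentences and a small programming change. Trial conduct and data collection are unaffected.

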8.5.3 Analysis of Secondary Endpoints

Egg reduction rate (ERR, %), calculated based on the arithmetic (and geometric) mean egg count per gram of stool (egp) will be calculated for each treatment arm after 14-21 days.

According to WHO guidelines, the group based egg reduction rates (ERR) after 14-21 days of PZQ drug administration is defined as:

ERR (%) = $100 \times (1\text{-arithmetic mean egg counts at post-baseline/arithmetic mean egg counts at baseline)$

To assess the corresponding ERRs for each treatment arm, Bootstrap resampling method with 10,000 replicates will be used to calculate 95% CIs for ERRs in each treatment arm.

Clinical cure rate assessed by POC-CCA assay for *S. mansoni* will be calculated (point estimation and 95% CIs) for each treatment arm.

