## 9 Changes to the Planned Analyses in the Clinical Trial Protocol

The statistical methods as described in the protocol were adopted.

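### The SAP reports the mean of the bootstrap replicates as the ERR_A point estimate, where the protocol defines ERR_A directly from the two arm means and uses the bootstrap only for the confidence interval

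*SAP*

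**What the plan says.** Protocol 8.5.3 defines the group ERR as 100 x (1 - ratio), where the ratio is "arithmetic mean egg counts at post-baseline/arithmetic mean egg counts at baseline". It gives the bootstrap one task: "Bootstrap resampling method with 10,000 replicates will be used to calculate 95% CIs for ERRs in each treatment arm". For the geometric-mean version it writes no equation.

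SAP 16.2.2 starts from the same quantity. ERR_A is the "relative difference expressed in percent between the post-treatment mean egg count and the pre-treatment mean egg count", taken relative to the pre-treatment mean. Missing counts are filled by LOCF. Baseline/end-of-study pairs are then resampled "with unrestricted random sampling, at a sampling rate of 1 and 10 000 replicates", and ERR_A and ERR_G are computed in each replicate. At that point the SAP departs from the protocol: "The arithmetic mean of the bootstrap sample will constitute the point estimate". The interval follows from the same replicates: "Corresponding 95% CIs will be determined using the percentile method, based on the bootstrap sample".

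The SAP nowhere says that the directly computed ERR will also be reported. SAP section 9 states: "The statistical methods as described in the protocol were adopted".

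**The concern.** ERR_A is one minus a ratio of two skewed means. The average of a ratio over resamples is not the ratio of the observed averages. Some resamples leave out the most heavily infected children, the baseline mean falls, and the ratio can jump. The tabulated estimate can therefore differ from the figure that the protocol's definition gives on the same data, and nothing in the SAP tells the reader so.

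The gap shrinks with cohort size and not with more replicates, so it matters most where n is smallest. Cohort C9 has 10 infants. The Part 2 interim analysis (SAP 8.3) is cut at 10 subjects, and secondary endpoints are among the results given to the SMC there.

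**Working it through.** **Inputs from the documents.** The two ERR definitions and the roles of the bootstrap are as set out above. Cohort sizes are 60 randomized and at least 50 evaluable per Part 1 arm, 30 in C8 and 10 in C9. Neither document states an expected ERR, an SD or a target precision for ERR, so there is no ERR figure of the plan's own to reproduce.

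**Formula.** Let x be the baseline count, y the end-of-study count and R = ybar/xbar. The direct estimate is 100(1 - R). To second order,

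bootstrap mean - direct ERR_A ≈ -100 x [R var(x) - cov(x,y)] / (n xbar²).

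The number of replicates does not appear in it.

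**Worked example** (illustrative counts, n=10). Baseline: 8, 12, 24, 36, 60, 96, 120, 240, 480, 1200. After treatment, the child with 60 has 60, the child with 120 has 100, and the other eight have 0.

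- Means: 2276/10 = 227.6 and 160/10 = 16. R = 160/2276 = 0.0703, so the direct ERR_A is 93.0%.
- var(x) = 175,729.6 - 227.6² = 123,927.8. cov(x,y) = 1,560 - 227.6 x 16 = -2,081.6.
- Predicted gap: -100 x (0.0703 x 123,927.8 + 2,081.6) / (10 x 51,801.8) ≈ -2.1 points.
- Actual bootstrap mean with 10,000 replicates: 89.9%, a gap of -3.0. The approximation understates the gap at this size.
- The same ten pairs repeated give a direct ERR_A of 93.0% at every n. The bootstrap mean is 92.2% at n=30, 92.5% at n=50 and 92.6% at n=60.

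The bootstrap mean does not correct bias. A bootstrap correction would subtract the estimated bias and move the other way: 2 x 93.0 - 89.9 = 96.1%. The SAP's estimate adds it.

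**Simulation.** Assumed: lognormal baseline with mean 150 epg, 50% or 75% egg-negative after treatment, and residual counts either unrelated to baseline or proportional to it. There were 300 cohorts per scenario with 2,000 replicates each. Average direct ERR_A was about 88% (75% egg-negative) or 76% (50%), so children still positive kept about 12/25 = 24/50 = 0.48 of the baseline level. Mean gap in percentage points:

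| Scenario | n=60 | n=50 | n=30 | n=10 | n=10, 5th to 95th percentile |
|---|---|---|---|---|---|
| CV 2, unrelated, 75% negative | -0.60 | -0.69 | -0.91 | -2.90 | -10.6 to +0.7 |
| CV 2, unrelated, 50% negative | -1.18 | -1.27 | -2.19 | -5.25 | -18.5 to +0.3 |
| CV 2, proportional, 75% negative | +0.05 | -0.03 | +0.07 | +0.18 | -2.7 to +4.3 |
| CV 2, proportional, 50% negative | -0.14 | +0.01 | -0.05 | +0.08 | -4.1 to +5.4 |
| CV 1, unrelated, 75% negative | -0.19 | -0.21 | -0.39 | -0.88 | -3.7 to +0.5 |
| CV 2, unrelated, 75% negative, 17% missing filled by LOCF | -0.35 | -0.59 | -1.01 | -2.14 | -9.4 to +4.1 |

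With smaller residual counts (30% of baseline level, CV 2, unrelated), the mean gap was about -0.4 to -0.8 points at n=50-60 and about -1.6 to -3.3 at n=10.

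For ERR_G as the SAP defines it, the mean gap was at most 0.4 points in every scenario.

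**The case against.** The strongest reply is that nothing in the trial turns on this. ERR is a secondary, descriptive endpoint and no hypothesis is tested. The only numeric efficacy criterion for dose selection in the documents is an observed cure rate above 70%, and no ERR threshold appears. The SMC sees ERR at the 10-infant look, but the protocol and SAP attach no numeric ERR rule to that decision. This stands.

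The gap is also small beside the uncertainty printed with it. With CV 2, the median absolute gap was about 2-3% of the 95% CI width at n=50-60 (widths of roughly 10 to 22 points) and about 4-5% at n=10. This stands too.

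Three stronger readings are tempting, and the documents do not support them:

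- A reader might infer that the SAP estimates the wrong quantity. It does not. Its own definition is the protocol's ratio, and the bootstrap mean estimates that ratio from the same pairs with an extra order-1/n error. Subject-level counts are to be listed, so a reader could still compute the direct value.
- A reader might infer that the result hangs on the random seed. With 10,000 replicates the Monte Carlo standard error is typically about 0.03 to 0.11 points. The percentile CI depends on the seed as well, and it would be kept.
- A reader might extend the point to ERR_G. The protocol writes no ERR_G formula to depart from, and the gap there is negligible.

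None of this answers the mismatch itself. Two current texts prescribe different point estimates for ERR_A, and SAP section 9 says that nothing changed.

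**Conclusion.** The point holds for ERR_A, as an undeclared change of estimator that adds small-sample bias. It is minor. In the Part 1 arms the average gap is about 1 point or less, so the between-arm picture should barely move. At n=10 an average gap of about -2 to -5 points is possible if residual counts are unrelated to baseline, and a small share of such cohorts would be off by more than 10 points. If residual counts are proportional to baseline, the average gap is about 0, although single small cohorts still move either way.

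These sizes rest on the assumed skew (CV 2) and baseline/post relation, neither of which the documents give. With CV 1 the gaps are well under half as large. If every child in a cohort is egg-negative, both estimates equal 100% and there is no gap. The documents do not support any claim that the primary cure rate or the stated dose-selection criterion is affected.

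**What to change.** In SAP 16.2.2, replace the sentence on the point estimate. ERR_A should be computed once, from the protocol 8.5.3 formula, on each arm's data after the planned imputation, and reported as the point estimate. For consistency, compute ERR_G once in the same way from the SAP's own definition. Keep the 10,000 paired replicates for the percentile 95% CI only.

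If the sponsor prefers the bootstrap mean, SAP section 9 should list it as a change from the protocol with a reason, and the direct ERR_A should be tabulated beside it.

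The cost is one sentence in the SAP and a small programming change. It needs no new data and no change to the design.
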